### **Methodology:**

#### *Inclusion criteria*

Patients will be screened and considered eligible for the study if they are:

1. between 18 and 74 years of age,
2. have stable coronary artery disease and diabetes mellitus, already on DAPT with aspirin and clopidogrel for at least 6 months,
3. not on any physician-prescribed medications or complementary/alternative therapies,

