***Null Hypothesis:***

There is no difference in response in patients with stable coronary artery disease on DAPT concerning PRUs on dapagliflozin.

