**Study Goals and Objectives:**

1. To describe platelet function profiles of patients with stable coronary artery disease on DAPT on dapagliflozin.

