#### *Exclusion criteria*

Patients are ineligible to participate if any of the following criteria are met:

1. presence of active internal bleeding or history of bleeding diathesis or clinical findings associated with an increased risk of bleeding,
2. history of ischemic or hemorrhagic stroke, transient ischemic attack, intracranial neoplasm, arteriovenous malformation, or aneurysm,
3. history of clinical and/or hemodynamic instability,
4. within 1 month of placement of a bare metal stent,
5. within 30 days of coronary artery bypass graft surgery or PCI without a stent placed,
6. planned coronary revascularization,
7. treatment with fibrin-specific fibrinolytic therapy <24 h or non-fibrin-specific fibrinolytic therapy <48 h,
8. use of an oral anticoagulation agent or international normalized ratio >1.5,
9. body weight <60 kg,
10. age >75 years,
11. hemoglobin <10 g/dL,
12. platelet count <100×10^6/µL,
13. creatinine >2 mg/dL,
14. hepatic enzymes >2.5 times the upper limit of normal,
15. pregnancy and/or lactation.

The study will undergo a formal approval process by the Campus Ethics Committee (CEC) of the University of the West Indies (UWI) and all patients are to provide written informed consent before participating in the study. The trial will be conducted by the Declaration of Helsinki and the International Conference on Harmonization (ICH) Guidelines for Good Clinical Practice

(GCP). Two clinical research associates (CRAs) will secure and assess the quality of the data and the university biostatistician will perform the data analysis after data lock. The CRAs will then deliver the database and the analysis results to the principal investigator (PI). Data will be coded per patient by first letter of first name, first letter of last name followed by numerical date of birth in the order of day, month, and year in a password-protected and encrypted database program in the office of Lecturer [name] at the Department of Clinical Medicine office, [name], Eric Williams Medical Sciences Complex.

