#### *Patient Interview and Case Report Form*

If a patient satisfies the selection criteria from the initial screening process, a physician or CRA-directed interview will then be administered. Demographic and anthropometric data will be recorded on a case report form (CRF). This will comprise the patient's medical and procedural history including any active medications.

Each patient will then be allocated via a computerized randomization program. Patients on DAPT for at least 6 months will be tested for platelet function testing with the P2Y12 VerifyNow assay at baseline. The patients will then undergo at least a 2-week course of dapagliflozin 10mg, followed thereafter by platelet function testing. The study will be randomized via a computer randomization program with a permuted block design and concealment allocation. It is also a controlled, prospective trial design, as group A serves to act as a baseline comparator group and group B has the desired antiplatelet strategy to be investigated over the longitudinal 2-week period. The study will also be blinded as patients will be unaware of their treatment assignments as well as the CRA or physician (Interventional Cardiologist) that performs the platelet function testing.

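### Two eligibility lines cannot be applied as written: inclusion 3 contradicts the aspirin and clopidogrel required by inclusion 2, and the platelet cut-off in exclusion 12 carries a unit error, presumed 1000-fold

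*Combined protocol and SAP*

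**What the plan says.** All references are to the combined protocol and SAP.

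**Inclusion criteria.** Item 2 admits patients with stable coronary artery disease and diabetes who are "already on DAPT with aspirin and clopidogrel for at least 6 months". Item 3 then requires them to be "not on any physician-prescribed medications or complementary/alternative therapies". The items form one numbered list, with no alternative between them and no exception clause.

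**Exclusion criteria.** Item 12 excludes patients with "platelet count <100×10 6" per microlitre, where the final 6 is a superscript exponent. Meeting any one exclusion makes a patient ineligible. Item 1 covers bleeding history and "clinical findings associated with an increased risk of bleeding" but gives no platelet count. Item 8 separately bars oral anticoagulants.

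**Elsewhere.** The Null Hypothesis concerns "patients with stable coronary artery disease on DAPT concerning PRUs on dapagliflozin". Study Goals and Objectives refers to "patients with stable coronary artery disease on DAPT on dapagliflozin". Patient Interview and Case Report Form says "Patients on DAPT for at least 6 months will be tested", and has active medications recorded on the case report form (CRF).

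**The concern.** Both lines decide who may enter the trial. If item 3 means what it says, the drugs that define the study population disqualify a patient from it. If item 12 means what it says, no human platelet count is high enough.

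In practice, site staff would have to work to some other rule, and that rule is not written down. For item 3, one person might allow DAPT alone, and another might allow DAPT plus the usual treatment for diabetes and coronary disease. The choice determines which patients can enrol. For item 12, the line is a bleeding-safety screen in patients already taking two antiplatelet drugs, so a missing threshold matters more than a slip in background text. Whatever rule staff adopt, the enrolled patients would not meet the criteria as printed.

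**Working it through.** **Inclusion 3 against inclusion 2**

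1. Item 2 requires current aspirin and clopidogrel. Item 3 requires no physician-prescribed medication.
2. The items are joint requirements, so a patient must satisfy both.
3. Assumption: the DAPT, or at least the clopidogrel, is prescribed by a physician. A patient who meets item 2 then fails item 3, and no patient on prescribed DAPT meets both.
4. Three sections outside the criteria (Null Hypothesis, Study Goals and Objectives, Patient Interview and Case Report Form) describe the patients as on DAPT. None states an exemption from item 3.
5. These sections establish that DAPT must be allowed. They do not say whether other drugs are allowed, and two places leave that open:
   - Exclusion 8 bars oral anticoagulants separately. That would be largely redundant if all prescribed drugs other than DAPT were already barred.
   - The CRF records active medications. This is weaker evidence, because DAPT alone would give something to record.

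**Exclusion 12**

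Input from the plan: 100×10^6 per microlitre.

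1. Printed cut-off: 100×10^6 = 100,000,000 per microlitre. There are 10^6 microlitres in a litre, so this is 100×10^6 × 10^6 = 100×10^12/L.
2. Presumed intended cut-off (an assumption; the documents do not give it): 100×10^3 = 100,000 per microlitre, which is 100×10^3 × 10^6 = 100×10^9/L.
3. Ratio: 100,000,000 / 100,000 = 1000.
4. The ratio is the same if the slip is in the volume unit. A cut-off of 100×10^6 per millilitre is 100×10^6 / 1000 = 100,000 per microlitre, the same presumed value.
5. Effect as printed: human counts are assumed to lie at about 150,000 to 450,000 per microlitre (not given in the documents). All of that range is below 100,000,000. Even a count of 1,000,000 per microlitre falls short by a factor of 100,000,000 / 1,000,000 = 100. The conclusion that everyone is excluded therefore does not depend on the exact range assumed.
6. No other section supplies a platelet threshold.

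**The case against.** The strongest reply is that neither error can do quiet harm. Read literally, each line enrols nobody, so neither can silently admit the wrong patients, and anyone screening the first candidate would notice. DAPT plainly defines the population, and a clinician would recognise the platelet figure as a misprint. On this view both are minor wording corrections. Most of that stands: staff would probably read around both lines. What remains is that the replacement rule is unwritten, and that for item 3 the documents do not show which rule was meant.

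A reader might be tempted by three stronger readings:

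- *Item 3 simply means no other medication.* That is a natural guess, but the documents do not establish it. Exclusion 8 points the other way, and the strict reading would bar glucose-lowering, statin and antihypertensive drugs in patients who have both diabetes and coronary disease.
- *The trial cannot recruit, or its result is compromised.* The documents do not support this. Nothing in either line changes the power, the Type 1 error or the treatment estimate.
- *The sponsor is known to have meant 100×10^9/L.* This is a presumption. A misreading of the unit when the PDF was converted to text cannot be wholly excluded either, although the exponent and unit appear clean.

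**Conclusion.** The point holds as a drafting correction to two operative eligibility rules, and it should be fixed.

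- Inclusion 3 contradicts inclusion 2, given only that the DAPT is physician-prescribed.
- Exclusion 12 as printed excludes every patient, given only that no human count approaches 100 million per microlitre. The 1000-fold size of the error rests on the presumed intended value. The protocol has no usable platelet threshold; exclusion 1 is a partial backstop through bleeding history and clinical signs.

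The status of background drugs other than DAPT cannot be settled from the documents, and only the sponsor can say.

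**What to change.** 1. **Inclusion 3.** Exempt at least the aspirin and clopidogrel required by item 2. The sponsor should confirm, in the same amendment, whether other background drugs for diabetes and coronary disease are barred or allowed, and the criterion should say which.
2. **Exclusion 12.** Correct the cut-off to below 100×10^3 per microlitre (100×10^9/L), for the sponsor to confirm.

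The cost is two lines of protocol wording. Active medications are already recorded on the CRF, and a complete blood count is already among the planned laboratory tests, so no new data item or assay is needed.

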#### *Exclusion criteria*

Patients are ineligible to participate if any of the following criteria are met:

1. presence of active internal bleeding or history of bleeding diathesis or clinical findings associated with an increased risk of bleeding,
2. history of ischemic or hemorrhagic stroke, transient ischemic attack, intracranial neoplasm, arteriovenous malformation, or aneurysm,
3. history of clinical and/or hemodynamic instability,
4. within 1 month of placement of a bare metal stent,
5. within 30 days of coronary artery bypass graft surgery or PCI without a stent placed,
6. planned coronary revascularization,
7. treatment with fibrin-specific fibrinolytic therapy <24 h or non-fibrin-specific fibrinolytic therapy <48 h,
8. use of an oral anticoagulation agent or international normalized ratio >1.5,
9. body weight <60 kg,
10. age >75 years,
11. hemoglobin <10 g/dL,
12. platelet count <100×10^6/µL,
13. creatinine >2 mg/dL,
14. hepatic enzymes >2.5 times the upper limit of normal,
15. pregnancy and/or lactation.

The study will undergo a formal approval process by the Campus Ethics Committee (CEC) of the University of the West Indies (UWI) and all patients are to provide written informed consent before participating in the study. The trial will be conducted by the Declaration of Helsinki and the International Conference on Harmonization (ICH) Guidelines for Good Clinical Practice

(GCP). Two clinical research associates (CRAs) will secure and assess the quality of the data and the university biostatistician will perform the data analysis after data lock. The CRAs will then deliver the database and the analysis results to the principal investigator (PI). Data will be coded per patient by first letter of first name, first letter of last name followed by numerical date of birth in the order of day, month, and year in a password-protected and encrypted database program in the office of Lecturer [name] at the Department of Clinical Medicine office, [name], Eric Williams Medical Sciences Complex.

#### *Patient Interview and Case Report Form*

If a patient satisfies the selection criteria from the initial screening process, a physician or CRA-directed interview will then be administered. Demographic and anthropometric data will be recorded on a case report form (CRF). This will comprise the patient's medical and procedural history including any active medications.

Each patient will then be allocated via a computerized randomization program. Patients on DAPT for at least 6 months will be tested for platelet function testing with the P2Y12 VerifyNow assay at baseline. The patients will then undergo at least a 2-week course of dapagliflozin 10mg, followed thereafter by platelet function testing. The study will be randomized via a computer randomization program with a permuted block design and concealment allocation. It is also a controlled, prospective trial design, as group A serves to act as a baseline comparator group and group B has the desired antiplatelet strategy to be investigated over the longitudinal 2-week period. The study will also be blinded as patients will be unaware of their treatment assignments as well as the CRA or physician (Interventional Cardiologist) that performs the platelet function testing.

#### *Blood Sampling, Phlebotomy*

Blood samples for platelet function testing will be collected at baseline before the patients are administered dapagliflozin (baseline sample). Blood will be drawn via an antecubital vein using a 21-gauge needle. The initial 5 mL of all blood samples will be discarded as medical waste as per the institution's policy (to avoid spontaneous platelet activation). Several laboratory tests will be performed including:

1. Complete Blood Count
2. Renal Function Profile
3. Hepatic Function Profile
4. VerifyNow P2Y12 PRU test assay - which will also be performed at the 2nd-week time point after patients have completed their assigned treatment schedules.

Overall, there will be 2 separate instances in which blood sampling/phlebotomy will be performed.

### *Aggregation Testing, Platelet Function Testing*

Citrated blood samples are processed by CRAs and study investigators. The platelet function assay to be utilized is the VerifyNow P2Y12 (VN-P2Y12) assay (Accriva, San Diego, California). In brief, the VN-P2Y12 assay is a rapid whole blood point-of-care device that reports results as P2Y12 reaction units (PRU) and percent inhibition of platelet aggregation (%IPA). Assays will be performed as per the instructions of the manufacturer previously described. Please see attached:

- <http://www.accriva.com/uploads/assets/clsi-procedures/14983-revf.docx>
- <http://www.accriva.com/uploads/assets/clsi-procedures/14982-revk.doc>

### **Safety Considerations:**

Overall, patient risk would be considered minimal.

The risks of phlebotomy coupled with treatment and management are:

1. Arteriospasm, Hematoma – sterile compression bandage will be done to achieve hemostasis monitoring of vital signs digital pulse oximetry to ensure perfusion of tissues, blood transfusions, Vascular Surgeon consultation for brachial artery repair, and/or luminal dilatation.
2. Nerve damage/injury- Orthopaedic management of possible injury to median nerve, evaluation, and follow-up in the clinic, and possible anti-inflammatory medications for nerve inflammation.
3. Infection- Debridement, microscopy, culture, and sensitivity as well as initiating empirical broad-spectrum antibiotics, and monitoring for signs of sepsis. If febrile or septic shock admission to hospital and commencement of intravenous fluids, intravenous antibiotics with possible ICU intervention.
4. Low risk: Phlebotomy: Vascular spasm, hematoma, local infection, Medium Risk Phlebotomy: nerve damage/injury (unlikely), Dapagliflozin: urinary tract infections, fungal infections, (rare-occasional, usually not life-threatening), Serious Risk Phlebotomy: hand surgery (exceedingly rare), Dapagliflozin: diabetic ketoacidosis, Fournier's gangrene, and hypoglycemia (very rare).

The study will be by the summary of risks and risk-reduction strategies outlined in Table 8 in the WHO Guidelines on Drawing Blood: Best Practices in Phlebotomy. Any serious adverse events (SAEs) will be recorded as per the Bleeding Academic Research Consortium (BARC) group definitions and reported to the Ethics Committee of the University of the West Indies within 24 hours. The patient will receive health care per the participating institution's guidelines and policies i.e. Cardiology Department at EWMSC, Mt. Hope, Trinidad & Tobago.

*Follow-up:*

Patients will be informed of their results in person, or if unavailable via telephone. They will also be provided with a hard-copy report of their platelet function profiles. They will also be informed on a scheduled basis of the management plan for any serious adverse events (SAEs) that may have unfortunately occurred as a result of their direct participation in the study.

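### Only serious adverse events are to be recorded, so the plan has no provision for capturing the dapagliflozin harms it rates as more frequent, urinary tract and fungal infections.

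*Combined protocol and SAP*

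**What the plan says.** All references are to the combined protocol and SAP.

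- **Safety Considerations, risk list.** Five dapagliflozin risks are named. Urinary tract and fungal infections are classed as medium risk and described as "urinary tract infections, fungal infections, (rare-occasional, usually not life-threatening". Diabetic ketoacidosis, Fournier's gangrene and hypoglycemia are classed as serious risk, the entry ending "and hypoglycemia (very rare". Overall patient risk is called minimal.
- **Safety Considerations, recording rule.** "Any serious adverse events (SAEs) will be recorded as per the Bleeding Academic Research Consortium (BARC) group definitions", with a report to the Ethics Committee within 24 hours.
- **Safety Considerations, Follow-up.** Patients are to be told of the "management plan for any serious adverse events (SAEs) that may have unfortunately occurred as a result of their direct participation in the study". Non-serious events are not mentioned.
- **Patient Interview and Case Report Form.** At the entry interview the CRF takes demographic and anthropometric data and the "medical and procedural history including any active medications".
- **Blood Sampling, Phlebotomy.** "Overall, there will be 2 separate instances in which blood sampling/phlebotomy will be performed". No enquiry about events is attached to either one.
- **Data Management and Statistical Analysis.** Generic tests for categorical variables are listed. No adverse event variable and no safety table by arm is named.
- **Expected Outcomes of the Study.** The results are meant to inform the Ministry of Health about adding dapagliflozin to the national programme as an antiplatelet adjunct.

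**The concern.** A recording rule limited to serious events tends to miss exactly the events that are more frequent and mostly mild. By the protocol's own grading, those are the urinary and fungal infections. Take a patient in the dapagliflozin arm who has a mild urinary infection part-way through the two weeks. Followed as written, the protocol asks nobody to enquire about it, gives it no described place on a form, and plans no table in which it would appear.

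What is at stake is the harm side of the evidence, not the platelet comparison. The trial is randomised with a comparator arm, so event counts by arm could be had at little cost. Without them, a report of few or no harms would reflect what was asked for. A reader weighing dapagliflozin as an adjunct would have a platelet result with almost no tolerability data beside it.

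**Working it through.** The protocol states no figure on this point, so there is none to reproduce. The check sets the named risks against the recording rule and then looks for any other place that could capture non-serious events.

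**Step 1. Named dapagliflozin risks against the rule (Safety Considerations).**

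| Risk | Protocol's class | Frequency wording | Covered by the SAE rule? |
|---|---|---|---|
| Urinary tract infection | Medium | rare to occasional | Only if serious |
| Fungal infection | Medium | rare to occasional | Only if serious |
| Hypoglycemia | Serious | very rare | Serious episodes only |
| Ketoacidosis | Serious | very rare | Within its scope as a serious event |
| Fournier's gangrene | Serious | very rare | Within its scope as a serious event |

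Two of five risks, the two with the higher frequency wording, are described as usually not life-threatening and so will often fall outside the rule. Splitting hypoglycemia into serious and non-serious episodes is this review's distinction; the protocol lists it only under serious risk. The ranking of the infections as more frequent rests on the frequency words alone and applies among dapagliflozin harms only.

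**Step 2. Other places where non-serious events could be captured.**

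- Study Goals and Objectives: platelet function only.
- Patient Interview and Case Report Form: entry data; no on-treatment event item is described.
- Blood Sampling, Phlebotomy: two blood draws; only the VerifyNow assay is stated to be repeated at week 2.
- Data Management and Statistical Analysis: no event variable.
- Quality Assurance: no DSMB; a general GCP commitment without an adverse event procedure.

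None supplies a rule, form field, question or time window for non-serious events.

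**Step 3. Would a formal between-arm test help?** Data Management aims for at least 16 patients. Sample Size Calculation gives n = 25 without saying whether this is per arm or in total. With equal arms (an assumption) that means 8, about 12, or 25 per arm. The two-sided Fisher p-value for k events in one arm and none in the other, with m per arm, is 2 × C(m,k) / C(2m,k):

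- m = 8: k = 4 gives 2 × 70 / 1,820 = 0.077; k = 5 gives 2 × 56 / 4,368 = 0.026.
- m = 12: k = 4 gives 2 × 495 / 10,626 = 0.093; k = 5 gives 2 × 792 / 42,504 = 0.037.
- m = 25: k = 5 gives 2 × 53,130 / 2,118,760 = 0.0502; k = 6 gives 2 × 177,100 / 15,890,700 = 0.022.

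So significance at 0.05 would need at least 5 against 0 with 8 or 12 per arm, and 6 against 0 with 25 per arm. The documents give no event rates. For scale only, the exact power of Fisher's test against an assumed 1% in the comparator arm is:

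| Assumed rate on dapagliflozin | 8 per arm | 12 per arm | 25 per arm |
|---|---|---|---|
| 5% | below 0.01% | 0.02% | 0.1% |
| 10% | 0.04% | 0.4% | 2.8% |
| 20% | 1.0% | 6.5% | 34% |

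A test would tell the reader almost nothing at these sizes. Plain counts by arm are the useful output.

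**The case against.** The strongest reply is that this is a small platelet-function study with no safety objective and no planned benefit-risk analysis, and that the gap leaves the PRU comparison untouched. That stands, and it limits the weight of the point. It does not remove it, because the protocol itself grades overall risk as minimal and wants the results to inform a national medication programme.

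A second reply is that the argument leans on silence. The CRF paragraph describes the entry interview and omits even the PRU results, so it is not a full list of fields. The Project Management table runs the CRF task for 20 months alongside sample collection, and the CRF template is not in the supplied text. An event page may exist. This is fair, and the finding is therefore limited to what the protocol provides for.

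Some stronger readings are tempting and are not supported:

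- *These infections would never be recorded.* A serious infection falls within the SAE rule, and staff working under GCP may note others. Neither is a collection procedure, but never is too strong.
- *Patients have no way to report events between visits.* Contact and consent pages were removed before review, and the protocol does not say how SAEs are ascertained. Nothing can be inferred about a missing contact number.
- *A given number of infections will be lost.* The protocol gives only frequency words, so any expected count would rest on an unsourced rate. Upper bounds for zero observed events would measure the small sample, not this defect.

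Finally, having the blinded assay operator ask about harms the protocol attributes to dapagliflozin could hint at allocation. That is a real cost, and the fix has to allow for it.

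**Conclusion.** The point holds as a gap in provision. The one recording rule covers serious events only, and no supplied section provides for recording or tabulating non-serious ones. The two dapagliflozin harms rated more frequent, and any non-serious hypoglycemia, would be captured only if serious or if noted informally.

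Its size is two of five named drug risks plus part of a third. No event count can be put on it from the documents. The consequence is confined to safety: the minimal-risk statement could not be checked against the trial's data, and there would be no adequate harm data alongside the use proposed under Expected Outcomes. The change should be made, but the primary platelet analysis does not depend on it.

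The conclusion assumes that the unseen CRF template and removed pages contain no event-collection procedure. If they do, the remaining task is to state it in the protocol and add the table by arm.

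**What to change.** 1. In Safety Considerations, widen the recording sentence to all adverse events, serious and non-serious, in both arms, from first dose (or the equivalent time point in the comparator arm) to the week-2 visit.
2. Add a short CRF page with one question for each of the five named dapagliflozin risks and one for bleeding, asked identically in both arms at the existing week-2 visit.
3. Protect blinding: complete the page after the VerifyNow assay has been run, or have existing staff who do not run the assay complete it.
4. In Data Management and Statistical Analysis, state that adverse event counts will be reported by randomised arm, descriptively and without a formal test.

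The same sentence has a separate problem: it ties SAEs to BARC, which the reference list describes as bleeding definitions. Both can be settled in one rewrite.

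**Cost.** Protocol wording, one CRF page, a few minutes per patient and slightly more data entry, with no extra visit or staff. A small unblinding risk remains, limited by asking after the assay.
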